4.1.3. Electronic Subject Diary during Screening Period

Subjects will be asked to use an electronic subject diary to self-report their bowel movement and rescue medication experiences each day. Subjects will be required to enter data on each bowel movement as soon as possible following completion. This data will include assessments of BM completeness, consistency, straining and urgency.

Each dosing episode of rescue medication will be entered. Instructions on how to complete the diary questions will be supplied in a separate manual.

4.2. Visit 2

Subjects will return to the study center as soon as possible after the 14 day Screening Period for Visit 2.

BM Entry Criteria – to be eligible for randomization, subjects must meet the following criteria related to their Screening Period BMs:

- average of fewer than 3 complete spontaneous bowel movements (CSBMs) per week during the 14 day Screening Period. A CSBM is defined as a bowel movement which has occurred with no rescue laxative use in the prior 24 hours and is accompanied by a sense of complete evacuation
- average of fewer than 6 spontaneous bowel movements (SBMs) per week during the 14 day Screening Period. An SBM is defined as a bowel movement which has occurred with no rescue laxative use in the prior 24 hours
- No more than 1 SBM with a Bristol Stool rating of 6
- No SBMs with a Bristol Stool rating of 7

Diary Compliance Criterion to be eligible for randomization, a subject must have completed an average of at least one Bowel Movement Diary entry per day for 5 or more days per week during the 14 day Screening Period

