9. DATA ANALYSIS

9.1. Sample Size

Six hundred subjects will be randomly assigned to BLI400 (21 g/day dose) or placebo in a ratio of 1:1 (300 BLI400, 300 placebo). The definition of a weekly responder is based on weekly assessments of complete spontaneous bowel movements (CSBMs).

Based on data from a previous laxative study (Lembo et al, 2011) utilizing this primary efficacy variable (percent of subjects who are responders), it is anticipated that approximately 20% of subjects would be classified as responders in the BLI400 arm, with a placebo response up to 10%. The proposed study size will have approximately 90% power to detect a difference of 10% between the active and placebo groups at a two-sided significance level of 0.05.

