9.3.1. Demographic and Baseline Characteristics

An analysis of baseline comparability of the following demographic and baseline characteristics for the treatment groups will be performed.

- Age (ANOVA)
- Gender (CMH Chi square)

- Race/ethnicity (CMH Chi square)
- Weight (ANOVA)
- Screening Period Constipation Status (ANOVA)

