9.3.2. Efficacy Analyses

Primary Efficacy Endpoint

The primary efficacy endpoint will be assessed on the basis of a binary outcome of overall treatment success or failure. The primary efficacy endpoint will be the proportion of subjects who are weekly responders for 9 out of the first 12 weeks of treatment, with at least 3 of these weeks occurring during weeks 9–12 of treatment. A weekly responder is a subject who has \geq 3 CSBMs and an increase from baseline of > 1 CSBM in that week. A CSBM is a bowel movement that occurs with no rescue laxative use in the previous 24 hours and that is accompanied by a sense of complete evacuation.

The following equation will be used to calculate the weekly CSBM frequency:

CSBM frequency = $7 \times (Number of CSBMs/number of days with non-missing CSBM assessments)$

If a subject has fewer than four days of data observed for a week, then that subject's data should be considered missing for that entire week and the subject considered a non-responder.

The primary efficacy endpoint will be analyzed using the CMH test controlling for the effect of study center. The presence of a treatment-by-center interaction will be investigated by the Breslow-Day test of homogeneity of the odds ratio. The strategy for pooling centers will be based on geographical considerations, with low enrolling centers pooled by geographic region. Details of any pooling performed will be documented prior to database lock and unblinding of the study.

No bowel movements that occur within 24 hours of a rescue bisacodyl (or other prohibited laxative) dose will be included in primary or secondary efficacy analyses.

Secondary Endpoints

Secondary endpoints will include the following:

- Overall response by gender and age group (< $65, \ge 65$ years, ≥ 75 years)
- Number of study medication doses taken per week
- Number of rescue doses taken per week (includes bisacodyl and other non-study laxative)
- % of subjects not meeting ROME criteria at the end of each treatment week
- BM Frequency per week (SBM and CSBM)
- BM Frequency per month (SBM and CSBM)
- BM Symptom Ratings per week (straining, consistency, urgency, Bristol score)
- BM Symptom Ratings per month (straining, consistency, urgency, Bristol score)
- Number of diarrhea episodes per week (diarrhea is defined as > 3 watery stools per day)

9.3.3.Safety Analyses

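### The primary CMH test adjusts for study center only; prespecifying adjustment for the age stratum and baseline CSBM frequency would be a low-cost precision gain of uncertain size

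*Combined protocol and SAP*

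**What the plan says.** Section 9.3.2 sets the primary test: "The primary efficacy endpoint will be analyzed using the CMH test controlling for the effect of study center". It adds a Breslow-Day check and geographic pooling of small centers, but names no other adjustment factor.

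Baseline CSBM frequency is nevertheless needed for every randomized subject. Entry under Section 4.2 requires an "average of fewer than 3 complete spontaneous bowel movements (CSBMs) per week during the 14 day Screening Period". The weekly responder rule in Section 9.3.2 requires at least 3 CSBMs and "an increase from baseline of > 1 CSBM in that week". Beyond those two uses, the only planned analysis of baseline severity appears to be the comparability check in Section 9.3.1, "Screening Period Constipation Status (ANOVA").

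Section 4.2.1 stratifies randomization by age (under 65, 65 and over); the primary test does not include that stratum. Section 9.3.2 also lists weekly and monthly SBM and CSBM frequencies as secondary endpoints without an analysis model.

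**The concern.** Baseline CSBM frequency is on the same scale as the outcome and is plausibly its best available predictor. The change-from-baseline clause does not cancel that link. On a full 7-day week a subject with baseline 0 must gain 3 CSBMs to respond, while a subject at 1.5 must gain 1.5. If baseline predicts response, a test that ignores it carries avoidable variance. The comparability ANOVA could then reveal a chance imbalance in severity that no planned analysis corrects.

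The age stratum raises a simpler point: a factor that constrained the randomization would normally appear in the analysis. For the continuous secondary endpoints, where baseline adjustment usually helps most, the plan is silent.

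**Working it through.** **Inputs from the document.** Section 9.1: 300 per arm; 20% versus 10% responders; "at a two-sided significance level of 0.05"; claimed "approximately 90% power to detect a difference of 10% between the active and placebo groups". Section 4.2: baseline below 3 CSBMs per week. Section 9.3.2: 9 of 12 weeks, with at least 3 in weeks 9–12. **Not in the document:** any correlation or R² between baseline CSBM and response, or any baseline CSBM distribution. Both are assumed below.

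**1. The plan's own power** (centers ignored).
- Pooled SE under the null = √(2 × 0.15 × 0.85 / 300) = 0.02915.
- SE under the alternative = √((0.16 + 0.09) / 300) = 0.02887.
- Uncorrected: z = (0.10 − 1.96 × 0.02915) / 0.02887 = 1.485, so power is 93.1%.
- Continuity-corrected (subtract 1/300 from the difference): z = 1.369, so power is 91.5%. Fisher's exact test gives 92.0%.

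The stated figure is met.

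**2. What adjustment buys.** Let R² be the share of within-arm outcome variance explained by baseline. Variance scales by (1 − R²), and the saving is 600 × R² subjects.

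| Assumed R² | Subjects saved of 600 | Power at 20% vs 10% |
|---|---|---|
| 0 | 0 | 93.1% |
| 0.02 | 12 | 93.6% |
| 0.05 | 30 | 94.2% |
| 0.10 | 60 | 95.3% |
| 0.115 | 69 | 95.6% |

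The largest gain shown is 95.6 − 93.1 = 2.5 points.

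**3. Which R² is plausible.** This was simulated with the entry limit, the responder rule and 10%/20% response. Subjects' CSBM rates were spread on the log scale (A: mean −1.2, SD 1.0; B: mean −0.5, SD 0.8). The latent correlation between a subject's screening and treatment rates was varied.

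| Latent correlation | R² of a flexible baseline term (A; B) | Subjects saved (A; B) |
|---|---|---|
| 0 | 0.0008; 0.0021 | 0; 1 |
| 0.2 | 0.0042; 0.0031 | 3; 2 |
| 0.4 | 0.0193; 0.0134 | 12; 8 |
| 0.6 | 0.0522; 0.0360 | 31; 22 |
| 0.8 | 0.1145; 0.0792 | 69; 48 |

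Two further simulations under other assumptions gave smaller savings: at most 9 subjects at 0.4 or below, 9–21 and 5–23 at 0.6, and 25–45 and 12–56 at 0.8. So 20 or more needs a correlation of about 0.6 or higher, and is not assured even there.

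**4. Shape of the relation.** On a full week, baselines below 2 need 3 CSBMs. A baseline of 2.0 or 2.5 needs 4, because the rise must exceed 1. In distribution B at correlation 0.4, response (arms combined) at baselines 0, 0.5, 1.0, 1.5, 2.0 and 2.5 was 10.6%, 14.2%, 18.3%, 22.2%, 17.9% and 20.8%. The relation rises, drops at 2, then rises again, so a single straight line fits it imperfectly.

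**5. Why regression and not finer CMH strata.** In simulation, crossing an assumed 20 centers with 4 baseline categories inside the CMH lowered power to 89–91.5%, against about 92.5% for center alone. With 15% response in both arms, type I error was 4.4% for the CMH and 4.9% for the baseline-adjusted logistic test.

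**6. Secondary frequencies.** Covariate adjustment cuts variance by r². For an assumed r of 0.2 to 0.5 that is 0.2² = 4% to 0.5² = 25%.

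**The case against.** The strongest reply is that nothing here is wrong. Omitting a prognostic covariate neither biases a center-stratified CMH test nor inflates its type I error, and the trial already has its stated power. That stands, and it limits the point to an improvement.

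A reader might infer that the plan is giving up a definite 20 to 70 subjects. The document does not support that. It would need an R² of about 0.033 to 0.117 (20/600 to 70/600), and no such figure is given. Restricting entry to baselines below 3, together with the drop at 2, could also weaken the association.

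A reader might also infer that the change is costless. It is not quite. The CMH cannot take a continuous covariate, so the adjusted result must come from a model whose covariate form, standardization and variance method have to be specified. A plain logistic odds ratio would also be conditional, which is why the standardized risk difference is proposed.

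Two smaller points stand. The baseline need not rest on 14 complete diary days, since Section 4.2 accepts entries on an average of 5 or more days a week. Section 9.4.3 also refers to a statistical analysis plan; no separate text of it was available in the document reviewed, so an adjusted analysis there cannot be excluded. If one exists, Section 9.3.2 only needs to be aligned with it.

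**Conclusion.** The point holds as an efficiency recommendation. The primary test controls for center alone, leaves out the randomization stratum and an already-derived baseline, and the secondary frequencies have no stated baseline-adjusted model. For the primary endpoint the benefit is about 0 to 70 of 600 subjects and about 0 to 2.5 power points at 20% versus 10%. It is under 20 subjects at a latent correlation of 0.4 or below. These sizes rest on assumed rate distributions and correlations. The gain from adding the age stratum was not quantified. The 4–25% variance reduction for the secondary frequencies likewise rests on an assumed correlation.

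Confidence is high that the factors are absent from Section 9.3.2 and low about the size of the gain. The document does not support reading this as an invalid test, a biased result or a shortfall in power.

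**What to change.** Before unblinding, amend Section 9.3.2 as follows.

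- Prespecify a logistic regression of overall response on treatment, pooled center, age stratum (<65, ≥65) and baseline CSBM frequency. Enter baseline as a flexible or categorical main effect that allows for the change at about 2, not as one linear slope.
- Report the standardized (marginal) risk difference with 95% CI, and state the variance method. Keep the center-stratified CMH as supportive. If the sponsor prefers the CMH as primary, name the adjusted model as a prespecified sensitivity analysis.
- Do not cross baseline categories with center inside the CMH.
- Analyze weekly and monthly SBM and CSBM frequencies with the matching baseline frequency as covariate.

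The cost is plan wording and a model-based result alongside the CMH. No new data, visits or subjects are needed.

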3.4. Study Treatments

BLI400 Laxative

BLI400 laxative will be provided polyethylene bottles containing enough study medication for approximately 30 days. The bottles will be equipped with a cap that can be used to measure 10.5 grams of BLI400. Using the provided measuring cap on the bottle, subjects will be instructed to mix 2 capfuls of study medication (approximately 21 g) in 4-8 oz of juice or other beverage and take once daily, preferably in the morning. Subjects that develop persistent diarrhea or loose stools will be allowed to adjust their dose down to 10.5g (1 capful) per day.

BLI400 placebo will be provided in identical polyethylene bottles containing regular maltodextrin.

Rescue Bisacodyl

Subjects will be dispensed bisacodyl tablets at each study visit. Subjects will be instructed to take 5 - 10 mg (1 - 2 tablets) of bisacodyl if they are experiencing severe discomfort due to their constipation, or have not had a BM in 4 days. No more than 6 tablets (30mg) of bisacodyl should be taken in a week.

If a subject does not have a bowel movement within 24 hours of taking a bisacodyl dose, a second dose should be taken. If after the second bisacodyl dose the subject does not have a BM within 24 hours, the subject should contact the site. The investigator should then consider having the subject return for an evaluation and/or discontinuing the subject from the study to seek alternative treatment.

All study medication is required to remain at room temperature 20°-25°C (68°-77°F); excursions permitted between 15°-30°C (59°-86°F).

All drug components will also have a clinical label containing a caution statement, study code, study sponsor and subject number.

Sites can view weekly summaries of subject diary data, including rescue bisacodyl use. Investigators should consider discontinuing subjects consistently taking more than 30mg of bisacodyl per week.

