3.5. Subject Selection

3.5.1. Inclusion Criteria

Subjects will be admitted to the study if they are:

- 1. Male or female subjects at least 18 years of age
- 2. Constipated, defined by the following adapted ROME II definition (Drossman et al, 2000):
 - A. Fewer than 3 spontaneous defecations per week and at least one of the following

symptoms for at least 12 weeks (which need not be consecutive) in the preceding

12 months:

a. Straining during > 25% of defecations

- b. Lumpy or hard stools in > 25% of defecations
- c. Sensation of incomplete evacuation for > 25% of defecations
- 3. If female, and of child-bearing potential, is using an acceptable form of birth control (hormonal birth control, IUD, double-barrier method, depot contraceptive, sterilized, abstinent, or vasectomized spouse)
- 4. Negative serum pregnancy test at screening, if applicable
- 5. In the Investigator's judgment, subject is mentally competent to provide informed consent to participate in the study

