4.1. Visit 1: Screening

At the screening visit, the following procedures will be undertaken:

- Subject is fully informed about the study and gives written agreement to study participation in the form of a signed informed consent form (refer to Section 4.1.1) and assign a subject number
- Assess eligibility (refer to inclusion/exclusion criteria)
- Review of medications
- Medical history including history of constipation (ROME criteria see inclusion #2)
- Physical examination
- Vital signs: including assessment of orthostatic hypotension (while seated and after standing for a minimum of 2 minutes) including height and bodyweight, pulse and temperature
- A 12-lead ECG will be performed by qualified, trained site personnel. ECG output must be reviewed by a physician investigator. Any clinically significant cardiac abnormalities identified on the ECG should disqualify a subject. Data from the ECG will be collected in the eCRF.
- Blood and urine samples will be collected for testing at a central laboratory, as shown below.

Chemistry: alkaline phosphatase, ALT, anion gap, AST, bicarbonate, blood urea nitrogen (BUN), calcium, chloride, creatine kinase (CK), creatinine, eGFR, GGT, HCG, inorganic phosphate, magnesium, osmolality, potassium, sodium, uric acid. CK-MB will be tested in samples where the CK value is greater than 2.5 times the upper normal limit.

Hematology: hematocrit, hemoglobin, platelets count, red blood cell count, white blood cell count (and differentials)

Pharmacokinetic (PK) Sampling: lactitol

Urinalysis: including electrolytes (sodium, potassium, magnesium, calcium), microscopic analysis, urine osmolality

Subjects with clinically significant laboratory abnormalities, deemed as a potential safety issue by the Investigator, may be discontinued at the Investigator's discretion.

- Provide the subject an electronic diary and review instructions with the subject in detail to ensure full understanding (refer to Section 4.1.3).
- Dispense rescue bisacodyl. Subjects will be allowed to take 5 10mg of bisacodyl if they are experiencing severe discomfort due to their constipation, or have not had a BM in 4 days.
- Instruct subject to maintain their normal dietary habits during study participation.
- Schedule the next study visit to occur after 14 full screening days.

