4.3. Treatment Period

4.3.1. Electronic Subject Diary during Treatment Period

Each day during the Treatment Period, subjects will complete their e-diary reporting. Subjects will report each bowel movement as it occurs along with related symptoms and characteristics (consistency, straining, urgency, completeness). Subjects will also report their daily study medication and rescue medication doses (if applicable) as they occur.

4.3.2. Treatment Day 1

Starting the morning of Treatment Day 1 (the day after randomization), subjects will measure two (2) capfuls of study medication and ingest it mixed in a beverage of their choice. When possible, subjects should take each dose at appromiately the same time every day (preferably in the morning). Subjects that develop persistent diarrhea or loose stools should contact their study center. Subjects with persistent diarrhea or loose stools will be allowed to adjust their dose down to 10.5g (1 capful) per day.

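### Does the weekly secondary endpoint on no longer meeting ROME criteria need a written weekly definition in the plan?

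*Combined protocol and SAP*

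**What the plan says.** Section 9.3.2, under Secondary Endpoints, includes the percentage "of subjects not meeting ROME criteria at the end of each treatment week". Nothing more is said about how it is scored.

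For constipation, the protocol uses the term in one other place. The Visit 1 list in Section 4.1 reads "Medical history including history of constipation (ROME criteria see inclusion #2", which sends the reader to inclusion criterion 2 in Section 3.5.1. That criterion asks for "Fewer than 3 spontaneous defecations per week and at least one of the following" of three symptoms: straining, lumpy or hard stools, or incomplete evacuation, each in more than 25% of defecations. Its time frame is "symptoms for at least 12 weeks (which need not be consecutive) in the preceding" 12 months. The other Rome definition, in Section 3.5.2, concerns irritable bowel syndrome.

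Three further rules bear on the point:

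- Section 3.4 allows rescue bisacodyl for subjects who have "severe discomfort due to their constipation, or have not had a BM in 4 days".
- Section 9.3.2 states: "No bowel movements that occur within 24 hours of a rescue bisacodyl (or other prohibited laxative) dose will be included" in the primary or secondary efficacy analyses.
- Section 4.2 (BM Entry Criteria) admits subjects with an "average of fewer than 6 spontaneous bowel movements (SBMs) per week during the 14 day Screening Period".

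On the data collected, Section 4.3.1 says: "Subjects will report each bowel movement as it occurs along with related symptoms and characteristics (consistency, straining, urgency, completeness").

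**The concern.** Read literally, the endpoint applies a 12-month history criterion at the end of every treatment week. Such a measure can hardly move within six months, even with complete relief.

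Read week by week, it has an awkward edge. A subject with no movement on days 1 to 4, rescue on day 5, one movement within 24 hours and none after has no countable movement that week. The frequency limb is met (0 is below 3), but each symptom share is 0/0. If 0/0 is programmed as not exceeding 25%, the subject falls outside the criteria and one of the worst possible weeks is reported as improvement. If frequency alone decides, the same week counts as constipated.

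Some subjects may also enter above the frequency limb, so they could be outside the weekly criteria before the first dose. The reported percentage, and possibly the treatment difference, would then rest on a choice that the plan does not record.

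**Working it through.** The plan attaches no figure to this endpoint, so there is none to reproduce. The power statement in Section 9.1 rests on CSBM responder rates and does not use it.

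**1. The look-back reading.** Inputs: at least 12 qualifying weeks in the preceding 12 months, taken as 52 weeks (Section 3.5.1), and final visit at Day 180 (Section 4.3.4), which is 180/7 = 25.7 weeks. Let q be the qualifying weeks in the 52 before treatment. After k weeks of complete relief, at least q − k remain in the window. Status cannot change while q − k ≥ 12, that is, q ≥ 12 + k.

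- k = 12: status is fixed if q ≥ 24.
- k = 26 (slightly generous to Day 180): status is fixed if q ≥ 38.
- A subject who qualified in all 52 weeks still has 52 − 25.7 = 26.3 qualifying weeks at Day 180, well above 12.

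This reading would need week-by-week data for the year before Visit 1. The diary is first issued at Visit 1 (Section 4.1), so those data do not exist. Any share of subjects changing status also depends on an assumed distribution. With q uniform on 12 to 52 and complete relief in everyone, the share by week 26 is 0% if the qualifying weeks are the most recent ones. It is 26/41 = 63% if they are the oldest (q from 12 to 37, out of 41 values). A range that wide reflects the assumption and says nothing about the trial.

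**2. The weekly reading.** The frequency limb of criterion 2 is already per week. Straining, consistency and completeness are recorded for each movement. The three symptom limbs can therefore be formed for any week with at least one countable movement, and only weeks with none need a rule.

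Let z be the share of such weeks in an arm (A = BLI400, P = placebo), and b the share not meeting the criteria among the remaining weeks.

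- Scored as meeting: D₀ = (1 − z_A)b_A − (1 − z_P)b_P.
- Scored as not meeting: D₁ = D₀ + z_A − z_P.
- Shift: D₀ − D₁ = z_P − z_A.

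The documents give neither z nor b. For illustration, assume b_A = 60% and b_P = 50%. With z_A = 5% and z_P = 10%, D₀ = 0.95 × 0.60 − 0.90 × 0.50 = 0.570 − 0.450 = 12.0 points, and D₁ = 0.620 − 0.550 = 7.0 points.

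| z_A / z_P (assumed) | D₀, points | D₁, points | Shift, points |
|---|---|---|---|
| 5% / 5% | 9.5 | 9.5 | 0 |
| 2% / 5% | 11.3 | 8.3 | 3.0 |
| 5% / 10% | 12.0 | 7.0 | 5.0 |
| 5% / 15% | 14.5 | 4.5 | 10.0 |
| 10% / 20% | 14.0 | 4.0 | 10.0 |

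If placebo has more such weeks, the odd scoring makes the drug look worse. It would favour the drug only if BLI400 had more weeks without a countable movement than placebo.

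**3. Subjects above the frequency limb at entry.** An average below 6 per week over 14 days means fewer than 12 SBMs, so at most 11, or 5.5 per week. Subjects between 3 and 5.5 may start outside the weekly criteria. Randomization spreads them over both arms, so they can dilute the difference but do not bias it.

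**The case for a change.** The strongest case for a change is that the scoring choice is unlikely to be neutral. An effective laxative should leave fewer weeks without a countable movement than placebo, so z_P − z_A is probably above zero. The obvious weekly adaptation also leaves details open: the 0/0 rule, the straining rating and stool form that count as symptoms, and the treatment of weeks with fewer than four diary days. The four-day rule in Section 9.3.2 is written for responder status and calls such a week both missing and non-responder. It does not say whether the week stays in this endpoint's denominator. Writing the definition would cost only words. Section 9.4.3 mentions a statistical analysis plan, but only for exclusions from the per-protocol population.

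The factual part of this stands: the text supplied has no weekly rule, no rule for weeks without a countable movement and no denominator for sparse weeks. The inference to a defect does not. Scoring an empty week as a success means treating an undefined share as evidence that symptoms are absent. No text says this will be done, and a statistician checking the output would be expected to reject it. Carrying over the four-day rule, so that a sparse week is never a success, is the natural step. The remaining cut-offs are ordinary programming detail for a descriptive measure.

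**Conclusion.** This is a gap in detail that analysts can be expected to fill sensibly, and it does not call for a change to the plan. The look-back reading can be set aside because the data for it do not exist. The endpoint's reference to each treatment week, together with the diary items, leads to a weekly status: SBM frequency below 3, and either no countable movement or a symptom in more than 25% of countable movements.

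The effect of choosing otherwise equals z_P − z_A. Its size is unknown: it starts at zero and is 3 to 10 points under the unequal rates assumed in the table, none of which come from the documents.

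The consequence is narrow. The endpoint is one of nine secondary bullets in Section 9.3.2 and is not named in the summary sheet's secondary list, which is expressly non-exhaustive. It has no stated test, alpha or place in a hierarchy. Weekly SBM and CSBM frequency and symptom ratings are secondary endpoints in their own right, so the components can be seen however the composite is scored. The primary analysis, power and safety are unaffected.

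The conclusion assumes that the weekly scoring is settled before unblinding, as is normal for programming detail. It would need another look only if the endpoint were given a confirmatory role.
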